11.4.1 Datasets to be Analysed, Analysis Populations

The intention-to-treat (ITT) approach includes all randomized patients. In order to account for the effects of antidepressant medication we will perform following analyses: The anticipated proportion of patients receiving additional antidepressants at some point during follow-up is estimated to be around 30%. The analysis of treatment efficacy of Omega-3 fatty acids needs to address that patients received additional antidepressants, and we propose the following analyses:

- Perform analysis according to intention to treat (ITT) principle by including all randomized patients according to their treatment groups and accounting for additional antidepressant use by jointly modeling the time to this event.
- Sensitivity analyses will be performed in which (i) all data are used as collected and actual missing data is multiply imputed based on MAR assumptions, (ii) all patients are used, but data upon additional antidepressant use are also considered missing and multiply imputed, (iii) entire follow ups from drop outs and participants initiating additional

antidepressants are removed (complete case, per protocol), and (iv) all participants are included according to randomization and delta-based multiple imputation is used for data after additional antidepressant use.

- Perform primary endpoint analysis considering the outcomes of patients with additional antidepressant prescription as missing values (from the time point of the antidepressant prescription).
- Both analyses described above will be prone to bias, because there might be differential antidepressant prescription, related to treatment group. In the efficacy analysis of the outcomes additional antidepressant prescription should not be ignored. We propose an approach in which the “missing” outcomes of patients with antidepressant prescriptions will be multiply imputed. By this approach, we mimic observations of depression scores that one would have received without antidepressant prescription. We plan to perform 10-fold multiple imputation. The missingness generating mechanism is considered to be “missing not at random” (MNAR), so the imputation method will need to address this. A method proposed by S. Jolani and S. van Buuren, 2013) is the “drawn indicator method” for missingness not at random.
- Sensitivity analyses of the results will reveal the dependence of the results on specific assumptions during the multiple imputation process.

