11.4.3 Secondary Analyses

Important CDRS-R-related outcome measures include response and remission. Remission is defined as a CDRS total score <28 and response is defined as a 30% drop in CRDS total baseline score (post placebo lead in). Participants using additional antidepressants, days on trial before the additional antidepressant, KIDscreen-CAT-27, and DIKJ will also be analyzed. Supportive endpoints include the number of days in the hospital and the amount of outpatient service use. For analysis details related to secondary and supportive outcomes of the primary trial reporting, please see the separate Statistical Analysis Plan document.

For further secondary outcomes, we will apply the same statistical strategy as for the primary outcome measures. Analysis will include changes in overall and subscores of the in chapter 9.2 listed secondary outcome instruments. We will analyze CDRS-R subscores, DIKJ, BHS, BAI, SIQ-Jr, IES-27, KIDscreen-CAT-27, PSS-10, and Resilience Scale scores and compare them between the treatment groups.

Furthermore, we'll run the following analyses to test our secondary working hypotheses:

- **WH3a:** We will test the effect of inflammatory mediators on the efficacy of omega-3 treatment by introducing an additional continuous factor (ratio between pro- and anti-inflammatory markers) into the linear regression model described in 11.4.2.
- **WH3b:** We will calculate an omega-3 index based on red blood cell Omega-3 fatty acids content and introduce an additional binary factor (n-6/n-3 Omega ratio < 3 vs. n-6/n-3 Omega ratio > 5) into the linear regression model described in 11.4.2.
- **WH3c:** We will test whether direct metabolites of EPA are a strong predictor of Omega-3 fatty acids by introducing additional continuous factors (levels of HETEs and E-series-resolvins at baseline) into the linear regression model described in 11.4.2

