where time t is considered a factor (while also investigating possibility of linearizing time effect) and randomized treatment group (intervention) and the interaction between randomized treatment group and time are included as fixed effects. The baseline values of the minimization factors age, gender, and hsCRP, as well as baseline antidepressant use and omega-3 index are included as covariates. The baseline outcome measure is modeled in the response, not as a covariate. The terms b_{i0} , b_{i1} , and b_{s0} represent participant-specific random intercepts and slopes and site-specific random intercepts. The random effects are assumed to be normally distributed and an unstructured covariance matrix will be assumed. The error term $\varepsilon_i(t)$ is assumed to be normally distributed with mean zero and variance σ^2 , independent of the random effects and is independent over time. An overall treatment effect for CDRS-R score at 36 weeks ($\beta_1 + \beta_{11}$) will be reported with a 95% confidence interval and corresponding p -value.

The competing survival models for time to event r (intervention dropout or study dropout) take the form:

$$\lambda_{ir}(t) = \lambda_{0r} \exp\{\gamma_1 \text{intervention} + \alpha_r m_i(t)\}$$

where the cause-specific Cox models include intervention as a time-independent effect and the estimated true trajectory of CDRS-R as a time-varying effect. The parameters α_r measure the strength of association between the longitudinal outcome and risk of the corresponding dropout event.

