7.1.2 Sensitivity analyses for the primary endpoint

1. **Typical ITT analysis:** In order to compare results with other trials, the linear mixed model part of the analysis model above will be applied to the full analysis set, with all participants analyzed as randomized. The data from intervention dropout participants will be used as observed, i.e, the outcomes observed while on non-randomized antidepressants will be used. The mixed model assumes that missing data is missing at random. This analysis is expected to be biased toward the placebo arm, as the number of participants requiring antidepressants is expected to be higher in the placebo arm and the additional antidepressant will improve outcomes.
2. **Modified ITT analysis:** The first sensitivity analysis will be repeated, but the data from intervention dropout participants will be considered missing in the mixed model upon non-randomized antidepressant initiation/dose increase. The responses of participants with missing data will be assumed similar to those with complete data and similar covariate characteristics. The bias resulting from imbalance in the use of non-randomized antidepressants across treatment groups is curtailed, but the amount of data available for analysis, and therefore power, is diminished.
3. **Typical PP analysis:** In order to address the efficacy estimand, the sensitivity analysis model above will be applied to all full analysis set data during which participants were 'on protocol'. This means the participants are adhering to the treatment they were randomized to and are not using additional antidepressants. Non-compliers and those taking non-randomized antidepressants are excluded completely (i.e., complete case analysis). This yields an estimate of efficacy that is unbiased under the MAR assumption. It assumes that participants with missing data (those with additional antidepressants and those not adhering to randomized treatment) would have had similar outcomes to participants completing the study in the same treatment arm and with similar baseline characteristics and score trajectories. However, the use of additional anti-depressants is not considered to be random across participants, but rather related to intermediate outcomes and possibly treatment assignment. Selection bias is then expected to affect this estimate. Additionally, the reduction in participants decreases the power to detect a treatment effect.

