4. **Delta-based multiple imputation for MNAR analysis:** The data after intervention dropout or study dropout is considered to be missing. Multiple imputation under MAR will be performed separately within each treatment arm (White et al 2011) using imputation models containing the minimization factors, baseline antidepressant use and omega-3 index. It will be assumed that participants initiating/increasing non-randomized antidepressant use would have had worse outcomes than observed had they not used the non-randomized antidepressant. A range of mean differences δ from a 25% increase in CDRS-R score (25% worse outcome) to a 100% increase (by 25% increments) in the CDRS-R score in the intervention dropouts as compared to the observed cases will be considered. Delta will then be added to the imputed

CDRS-R scores for the participants with intervention dropout. Results will be combined using Rubin's rule. This is repeated for each delta.

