These continuous outcomes will each be assessed using ANCOVA linear regression models with the 36-week measurement as the outcome, treatment arm as the effect of interest, and the baseline measurement, antidepressant use, omega-3 index, CDRS-R score, and the minimization factors age, gender, and hsCRP as covariates.

The treatment coefficient denotes the mean difference in outcome score across the treatment groups. The null hypothesis that the mean scores are equal across treatment groups will be rejected

if the 95% confidence interval for the treatment group coefficient does not include 0. If the 95% confidence interval for the treatment group coefficient is above 0 for KIDscreen-CAT-27 (below 0 for DIKJ), omega-3 treatment will be considered superior with respect to its effect on quality of life (depressive symptoms).

These models will include data from all randomized participants and analyze the participant data according to the treatment arms participants were randomized to (as-randomized). Data after intervention dropout will be considered missing. Multiple imputation under MAR will be used to impute scores at 36 weeks for study and intervention dropouts. MI will be performed separately within each treatment arm (White et al 2011) using imputation models containing the minimization factors, baseline antidepressant use, omega-3 index, and baseline score. As for the primary outcome, a delta-based sensitivity analysis approach will be used to address MNAR.

Sub-domains will be described with tables or figures.

The final confirmatory secondary outcome is:

- the time on trial before initiation of new or increased antidepressant use (intervention dropout).

A Kaplan Meier approach will be used to estimate unadjusted median time to this event overall and per treatment arm. A log rank test will be used to compare time to intervention dropout across treatment arms.

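### The imputation models listed for week-36 DIKJ and KIDscreen name only baseline variables, although the SAP ties antidepressant starts to intermediate scores; naming the interim scores is a cheap improvement

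*SAP*

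**What the plan says.** SAP 7.2.1 analyses DIKJ and KIDscreen at week 36 by ANCOVA. For participants who start or increase an antidepressant, "Data after intervention dropout will be considered missing". The week-36 score is then multiply imputed under MAR, separately by arm, "using imputation models containing the minimization factors, baseline antidepressant use, omega-3 index, and baseline score". The list holds no post-baseline variable. It also lacks baseline CDRS-R, which is a covariate in the ANCOVA itself.

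On why antidepressants are started, SAP 7.1.2 (item 3) says that "the use of additional anti-depressants is not considered to be random across participants, but rather related to intermediate outcomes". In the joint model of SAP 7.1, each dropout hazard depends on the current CDRS-R trajectory, through parameters that "measure the strength of association between the longitudinal outcome and risk of the corresponding dropout event". SAP section 1 anticipates about 30% starts overall and more in the control arm. It gives no split by arm.

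The omitted information is collected. CDRS-R is measured at baseline and weeks 6, 12, 24 and 36 (SAP 5.1). DIKJ is listed at week 6 (Protocol 9.3.3) and, in the schedule, also at weeks 12 and 24. KIDscreen is not in the week-6 list; the schedule, as far as it can be read, has it at week 12.

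For MNAR, SAP 7.2.1 refers back to the delta method of the primary outcome. SAP 7.1.2 (item 4) defines that as a worsening from 25% "to a 100% increase (by 25% increments) in the CDRS-R score in the intervention dropouts". The two scales run in opposite directions: when the interval for the treatment coefficient "is above 0 for KIDscreen-CAT-27 (below 0 for DIKJ), omega-3 treatment will be considered superior".

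**The concern.** MAR is a statement about what has been conditioned on. If starts follow how the participant is doing at the time, starters are doing worse than others with the same baseline values. A regression on baseline values alone then imputes their week-36 scores too favourably. When one arm has more starters, that arm is flattered more, and the contrast is biased. Interim scores observed before the start carry much of the missing information, and they also make the imputations more precise.

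Two confirmatory secondary endpoints are affected. The delta check inherited from CDRS-R also needs translating, because a literal increase on KIDscreen would be an improvement.

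**Working it through.** **1. The plan's own figure.** The documents state no power for DIKJ or KIDscreen. The nearest figure is in SAP 6.1: SMD 0.4, 80% power, two-sided 0.05, 111 per arm. A two-sample t-test gives 99.08 per arm, and 99.08/0.90 = 110.1, so 111. The figure reproduces if the 10% loss of SAP 6.2 is applied.

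**2. Inputs.** From the documents: about 30% starts; about 20 participants starting before week 6 (Protocol 6.3.2); 10% loss; 110 per arm; 50 imputations. Assumed: score means, SDs, correlations, the strength of the link between score and start, and every split by arm.

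**3. Simulation with the SAP's hazard form (300,000 per arm).** CDRS-R means are 55/48/44/41/38. Random intercept, slope and error SDs are 7/9/7, so the week-36 SD is √(49+81+49) = 13.4. The second outcome is on the same scale, with random effects correlated 0.7. The true effect is 5.3 points (5.3/13.4 = 0.40 SD). The start hazard is proportional to exp(α × latent current CDRS-R), and 30% of starts fall before week 6. Change in the estimated effect (%) at α = 0.3, 0.6, 0.9 per 10 points:

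| Starts %, placebo/omega-3 | Listed predictors | Plus interim DIKJ and CDRS-R | KIDscreen visit pattern |
|---|---|---|---|
| 35/25 | −4, −10, −12 | 0, −3, −4 | −1, −4, −4 |
| 40/20 | −10, −18, −24 | −3, −4, −7 | −3, −6, −9 |
| 30/30 | +1, 0, −2 | not run | not run |
| 25/35 | +4, +9, +12 | +1, +3, +3 | not run |

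Hand check: if starters in both arms are imputed e points too well, bias = (difference in start rates) × e. With the listed predictors, e for placebo starters is 2.2 to 6.1 points. At 35/25 the bias is 0.10 × 2.2 = 0.22 to 0.10 × 6.1 = 0.61 points, or 4 to 12% of 5.3. At 40/20 it is 0.44 to 1.22 points, or 8 to 23%. With interim scores e falls to 0.5 to 1.9 points.

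**4. Power in the same set-up** (110 per arm, 10% random loss, 50 imputations, α = 0.6, 1,500 trials, Monte Carlo SE up to 1.3 points). At 35/25: 60% with the listed predictors, 71% with interim DIKJ and CDRS-R, 69% with the KIDscreen pattern. At 40/20: 51%, 69% and 67%. With no true effect, superiority is declared with the listed predictors in 1.4% (35/25) and 0.5% (40/20) of trials, against a nominal 2.5%.

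**5. A second simulation with a different start model** (log-odds of start 1 to 2 per SD of current score, baseline to week-36 correlation about 0.4 to 0.6, 400 to 600 trials, 15 to 20 imputations). The true effect is −0.40 SD; percentages are bias/0.40.

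| Starts % | Bias, listed | Bias, interim | Power, listed / interim |
|---|---|---|---|
| 25/21 | +0.012 (3%) | −0.002 | 0.81 / 0.87 |
| 35/22 | +0.036 (9%) | −0.007 | 0.71 / 0.84 |
| 32/20, steeper link | +0.051 (13%) | −0.006 | 0.69 / 0.83 |
| 36/17, weaker correlation | +0.089 (22%) | +0.002 | 0.52 / 0.72 |
| 34/16 | +0.095 (24%) | −0.003 | 0.49 / 0.70 |
| 40/23, starts unrelated to score | none | none | 0.78 / 0.84 |

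The Monte Carlo SE of the bias is at most 0.008 SD. This set-up assumes MAR given the interim scores, so the near-complete repair is partly built in. In step 3 starts follow the latent trajectory, and there the repair is only partial.

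**6. Delta check.** One common worsening delta in both arms shifts the contrast by delta × observed mean × (placebo start rate − omega-3 start rate). For DIKJ, assume mean 20 and SD 8. At 36/24, +25% gives 0.25 × 20 × 0.12 = 0.6 points (0.075 SD) toward omega-3, and +100% gives 2.4 points (0.30 SD). With equal starts the shift is 0. At 25/35 it is 0.25 × 20 × 0.10 = 0.5 points per step against omega-3. DIKJ has 26 items scored 0 to 2, so its maximum is 52. At +100% with mean 20, any starter imputed above 32 leaves the scale.

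**The case against.** The strongest reply is that this is a gap in specification. The SAP says what the models contain, not what they exclude, so a statistician could add interim scores without departing from it. That stands in part. But the sentence names the baseline score, imputes week 36 only, and leaves out even a covariate of the analysis model, so following it literally is a real possibility.

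Three further replies stand. The inputs are assumed, and with equal starts the bias is within 2%. Much of the power loss is the bias seen again: with empirical SEs of 2.08 (listed) and 2.00 (interim) at 35/25 and an unbiased effect of 5.3, power would be Φ(5.3/2.08 − 1.96) = 72% against Φ(5.3/2.00 − 1.96) = 75%, so precision explains about 3 of the 11 points. And the roughly 20 participants who started before week 6 have no earlier follow-up score to use.

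A reader might infer more than the documents support:

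- *That the imputation favours omega-3.* Under the SAP's own expectation it works against omega-3. It favours omega-3 only if omega-3 has more starters, and then a common worsening delta moves the contrast the other way.
- *That the delta has no sign or size here.* SAP 7.2.1 carries over both the direction, worse, and the 25 to 100% range. Only the translation to KIDscreen and the scale limits are open. The +100% end is a stress value; the superiority rule is stated for the ANCOVA.
- *That an analysis keeping scores after antidepressant start is required.* Protocol 11.4.1 plans one in which "all data are used as collected and actual missing data is multiply imputed based on MAR assumptions", and Protocol 11.4.3 says "For further secondary outcomes, we will apply the same statistical strategy as for the primary outcome measures". But 11.4.3 leaves the details to the SAP, and the SAP does not assign its treatment-policy estimand to DIKJ or KIDscreen. Setting later scores to missing fits a hypothetical target, so the as-collected analysis answers a different question.
- *That remission and response share the defect.* There the SAP imputes the CDRS-R series, which most naturally includes earlier visits. This needs confirming only.

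**Conclusion.** The point holds in this limited form. For DIKJ and KIDscreen, the listed imputation model omits collected scores that the SAP itself connects with antidepressant starts. Across both simulations a 0.4 SD effect shrinks by roughly 3 to 13% with a moderate excess of placebo starts and by 10 to 24% with about twice as many. It is nearly unbiased with equal starts and 4 to 12% too large at 25/35. Adding interim scores brings the first two ranges to 0 to 4% and 3 to 7% for DIKJ, slightly more for KIDscreen, in the harder of the two set-ups. These sizes depend on assumed score parameters and assumed splits by arm; the documents fix only the overall 30%.

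In the expected case the consequence is lost power, not a false-positive risk. Some precision is lost even when starts are unrelated to score (0.78 against 0.84).

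One limit of the delta check should be understood: with more placebo starters, a common worsening delta can move the contrast only toward omega-3, so in that case it is not a less favourable test. This is a cheap improvement to two secondary analyses.

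**What to change.** In SAP 7.2.1, state that each imputation model also contains the outcome's own interim scores observed before dropout (DIKJ weeks 6, 12 and 24; KIDscreen week 12), together with baseline and interim CDRS-R. Confirm that baseline and earlier CDRS-R visits enter the imputations for remission, for response and for the CDRS-R delta analysis in 7.1.2.

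For the delta check, state that worse means a decrease on KIDscreen, and apply scale limits (DIKJ maximum 52). Note in the SAP that with more placebo starters this check moves only toward omega-3. A further scenario, such as a delta in the omega-3 arm only or an as-collected analysis labelled with its own estimand, is optional.

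The cost is a few sentences and some programming, with no new data. The gain will be small for the roughly 20 participants who started antidepressants before week 6.

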Omega-3 Fatty Acids as First-Line Treatment in Pediatric Depression

Statistical Analysis Plan for [name], [name]

[name] ([contact])

[name]

Version 1.0 of May 23, 2022

List of abbreviations

AD	antidepressant
AE	adverse event
CDRS-R	Children's Depression Rating Scale - Revised
DIKJ	Children's Depression Inventory (Depressionsinventar für Kinder und Jugendliche)
EPA	eicosapentaenoic acid
KIDscreen-CAT-27	quality of life questionnaire
pMDD	pediatric major depressive disorder
SIQ-Jr	Suicide Ideation Questionnaire-Junior
SUSAR	Suspected Unexpected Serious Adverse Reaction

Introduction

1 Type of trial

This is a 36-week multi-center 1:1 randomized, double-blind, placebo-controlled, two-armed, parallel group study investigating the superiority of EPA-rich Omega-3 to placebo in the treatment of children and adolescents with pediatric major depressive disorder. The randomization included a minimization algorithm based on the following factors: site, age (8-12 vs. 13-18), gender (male vs. female), and hsCRP (<1 mg/l; 1-3 mg/l; >3mg/l). For sites offering both in- and out-patient care, in-/out-patient type was used as an additional minimization factor. The trial aimed to recruit children/teenagers between 8 and 18 years old with a primary diagnosis of major depressive disorder (DSM-IV, K-SADS-PL) and at least moderate depressive symptoms (CDRS-R ≥ 40).

In order to include a representative sample of moderately and severely ill children with major depressive disorders, the use of clinically required SSRIs is permitted. The anticipated proportion of patients receiving additional antidepressants at some point during follow-up is estimated to be around 30%. The use of additional antidepressants is expected to influence primary outcome measurements and be influenced by treatment group, with greater antidepressant use hypothesized in the control arm. Antidepressant use may therefore bias the estimation of the omega-3 treatment effect.

2 Scope of the statistical analysis plan

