5.2 Secondary endpoints

5.2.1 Confirmatory secondary endpoints

- Remission (CDRS-R total score less than or equal to 28) at any point during the 36 weeks of trial observation
- Response (30% reduction in CDRS-R total score) at any point within 12 weeks from baseline
- Participants newly initiating antidepressant medication (or newly increasing dose if on antidepressant at baseline) at any point during the 36 weeks of trial observation
- Number of days on trial before new antidepressant initiation (or new antidepressant dose increase if on antidepressant at baseline)
- KIDscreen-CAT-27 overall quality of life score at 36 weeks
- DIKJ depression score at 36 weeks

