6.2 Difference in Proportion of Responders

A two-proportion z-test would require 97 participants per treatment arm to have 80% power to detect a difference in response of 20% (with 60% response in the treatment group and 40% response in the control group) at the 0.05 two-sided significance level. Accounting for a 10% loss to follow-up results in a total sample size of 216 participants.

7 Statistical analyses

Analysis sets The following analysis sets are defined in accordance with the ICH-E9 guidelines:

- The full analysis set (FAS) includes all randomized subjects. The FAS will be used for 'as randomized' evaluation. Only in exceptional cases may subjects be excluded from the FAS. In such cases the reason for exclusion will be justified and documented.
- The safety analysis set includes all randomized subjects receiving at least one dose of randomized treatment. The safety analysis set will be used for 'as treated' evaluation.

Baseline comparability of randomized groups Baseline descriptive variables of participants (including antidepressant use) will be summarized overall and by treatment arm using suitable measures of central tendencies and variability for continuous data (means or medians, SD or IQR) and frequencies and proportions for categorical data. No hypotheses are tested.

The number of participants lost to follow-up, initiating antidepressants, and adhering to the protocol will each be tabulated by treatment arm and visit. Baseline characteristics will also be summarized across the groups of participants completing the trial, lost to follow-up, and initiating antidepressant use.

General statistical considerations Statistical analysis results will generally be presented as point estimates with two-sided 95% confidence intervals. A limited number of analysis results will additionally be reported with p -values, which will be interpreted as indicative of superiority when the value is less than 5% and the estimated treatment contrast favors the omega-3 treatment arm.

Descriptive statistics for all efficacy and safety endpoints will be presented according to treatment arm.

The baseline values are collected at visit 1 (0 weeks), which is the first week after the lead-in phase. Further measurements are taken at visits 2 through 5 at 6, 12, 24, and 36 weeks.

The clinical trials registry number (03167307) will be used as a seed number, if needed.

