7.1 Primary endpoint

- CDRS-R total score from baseline (post-placebo-lead-in) to week 36

The primary analysis consists of a joint model linking (1) a linear mixed effects model for CDRS-R total score over time with (2) a Cox proportional hazards model for the risk of the event new initiation of or increase in antidepressant use (intervention dropout) and (3) a Cox proportional hazards model for the risk of study dropout as a competing event. This assumes that whether a participant has missing data and at what time this occurs contains additional information that should be taken into account and corresponds to an MNAR missing data mechanism.

Participants are censored at whichever occurs first of: antidepressant initiation/increase, loss to follow up, consent withdrawal, and study exit due to non-adherence. Participants lost to follow up, withdrawing consent, and exiting the study (as per protocol) due to non-adherence are considered alike and these events considered one event type: study dropout.

The linear mixed effects model for the longitudinal CDRS-R total score outcome $Y_i(t)$ measured at time t for participant i takes the following form:

$$\begin{aligned}
 Y_i(t) &= m_i(t) + \varepsilon_i(t), \\
 m_i(t) &= \beta_0 + \beta_1 \text{intervention}_i + \beta_2 t_{base} + \beta_3 t_{6weeks} + \beta_4 t_{12weeks} + \beta_5 t_{24weeks} + \beta_6 t_{36weeks} \\
 &\quad + \beta_7 t_{base} * \text{intervention}_i + \beta_8 t_{6weeks} * \text{intervention}_i + \beta_9 t_{12weeks} * \text{intervention}_i \\
 &\quad + \beta_{10} t_{24weeks} * \text{intervention}_i + \beta_{11} t_{36weeks} * \text{intervention}_i \\
 &\quad + \beta_{12} \text{age}_i + \beta_{13} \text{gender}_i + \beta_{14} \text{hsCRP}_i \\
 &\quad + \beta_{15} \text{antidepressant} + \beta_{16} \text{omega-3 index} \\
 &\quad + b_{i0} + b_{i1}t + b_{s0},
 \end{aligned}$$

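### SAP 7.2.1 gives time to new or increased antidepressant use only a Kaplan-Meier median, which is not expected to be reached overall or on omega-3, and a log-rank p-value, so the endpoint has no treatment effect estimate

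*SAP*

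**What the plan says.** SAP section 5.2.1 lists as one confirmatory secondary endpoint: "Number of days on trial before new antidepressant initiation (or new antidepressant dose increase if on antidepressant at baseline". A separate endpoint in the same list is whether the event occurs "at any point during the 36 weeks of trial observation".

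For the timing endpoint, section 7.2.1 specifies two things: "A Kaplan Meier approach will be used to estimate unadjusted median time to this event overall and per treatment arm" and "A log rank test will be used to compare time to intervention dropout across treatment arms". It names no hazard ratio, no week-36 estimate and no restricted mean. It gives no alternative if the median is not reached, and it does not say how study dropouts are handled.

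Other relevant statements:

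- SAP section 1: "The anticipated proportion of patients receiving additional antidepressants at some point during follow-up is estimated to be around 30" per cent. This is one pooled figure, "with greater antidepressant use hypothesized in the control arm".
- SAP section 6.2, on response: "Accounting for a 10% loss to follow-up results in a total sample size of 216 participants".
- SAP section 7, general statistical considerations: results are normally point estimates with two-sided 95% confidence intervals, and p-values are an addition for a limited number of analyses.
- SAP section 7.1: the primary joint model includes "a Cox proportional hazards model for the risk of study dropout as a competing event" and treats the occurrence and timing of missing data as informative.
- SAP section 7.2.1, binary version of the event: per-arm proportions with 95% CIs and an adjusted risk ratio, with imputation for patients who leave the study before the event.

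**The concern.** A Kaplan-Meier median exists only if the curve falls to 0.50 during follow-up. If about 30% of patients have the event, the curve ends well above that. Without a median, the plan leaves only a log-rank p-value, which says nothing about the size or precision of a difference. The other confirmatory secondary endpoints in section 7.2.1 each have an adjusted effect measure, a confidence interval and a rule for superiority. This one has none of the three.

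Study dropout raises a second, smaller issue. It is informative in the primary model, imputed in the binary version of the same event, and not mentioned for the timing endpoint. Protocol section 5.2 (WH 2d) expects more and earlier placebo dropout through lack of efficacy, which could also drive antidepressant starts.

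**Working it through.** **Inputs.** Event share e = 0.30, pooled (SAP section 1). Dropout share d = 0.10 (SAP section 6.2). Follow-up 36 weeks. 110 per arm (Protocol synopsis). The SAP states no figure for this endpoint. The calculation that supplies the 10% reproduces: 97 per arm for 60% against 40% at 80% power; 97/0.90 = 107.8, so 108 per arm and 216 in total.

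**Step 1: pooled curve at week 36.**

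- No dropout: S = 1 − 0.30 = 0.70.
- Constant, proportional hazards for event and dropout: S = (1 − e − d)^(e/(e+d)) = 0.60^0.75 = 0.68.
- Extreme case, all dropout before any event: S = 1 − e/(1 − d) = 1 − 0.30/0.90 = 0.67.

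With e held at 0.30, S reaches 0.50 only if dropout is 56% (proportional timing) or 40% (extreme case).

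**Step 2: chance that a median is reached.** 4,000 simulated trials, 110 per arm. Total hazard per arm is −ln(1 − e − d)/36 per week, split between event and dropout in the ratio e : d. The pooled share is kept at 30%. The arm splits, and dropout above 10%, are assumptions because the documents give neither.

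| Starts, placebo / omega-3 | Dropout | Placebo | Omega-3 | Pooled |
|---|---|---|---|---|
| 30% / 30% | 10%, 20%, 30% | 0%, 0.02%, 0.7% | 0%, 0.08%, 0.65% | 0% throughout |
| 40% / 20% | 10%, 20%, 30% | 7%, 21%, 49% | 0% throughout | at most 0.02% |
| 45% / 15% | 10%, 20%, 30% | 32%, 61%, 87% | 0% throughout | at most 0.05% |

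In the unequal splits the omega-3 median was never reached, so no difference in medians could be formed even when placebo reached its own.

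**Step 3: check against early trial data.** Protocol section 6.3.2 reports about 20 starts in the first 6 weeks, and section 6.2 reports 21 dropouts before the first follow-up among 225 randomised. Using 225 as the denominator for both (an assumption for the starts), e = 20/225 = 0.089 and d = 21/225 = 0.093. Then S at week 6 = (1 − 0.182)^(0.089/0.182) = 0.907. At constant hazard (an assumption), S at week 36 = 0.907^6 = 0.555, or 44% started, and the pooled median falls near week 42, after follow-up ends. If the arm hazards average to this rate with a hazard ratio of 0.67, placebo reaches its median near week 35, while omega-3 is at about 38% by week 36 and does not.

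**Step 4: the log-rank test.** Expected events: 0.30 × 220 = 66. Power = Φ(√(66/4) × |ln HR| − 1.96).

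- 35% against 25% (assumed): HR = ln 0.75/ln 0.65 = 0.67, power 38%.
- 40% against 20% (assumed): HR = ln 0.80/ln 0.60 = 0.44, power 92%.

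The test is usable. Under the smaller difference, however, a non-significant result would be likely, and a p-value alone would not show which effects remain plausible.

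**Step 5: weight of the dropout rule.** At 30% observed starts and 10% dropout, one minus Kaplan-Meier is 1 − 0.68 = 31.8%. The share ever starting by week 36 lies between 30% (no dropout starts) and 30% + 10% = 40% (all do).

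**The case against.** **The event already has an effect estimate.** The binary endpoint in section 7.2.1 gives per-arm proportions and an adjusted risk ratio with 95% CI. This stands, and it limits the damage: the trial does not lack an estimate for antidepressant starts. It answers whether, not when, and the SAP lists timing as its own confirmatory endpoint. The Cox part of the primary joint model does not fill the gap either. Its treatment coefficient is conditional on the CDRS-R trajectory, and the SAP states no plan to report it.

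**A median that is not reached is an ordinary result, and the test is unaffected.** True, and nothing here questions the log-rank test. The gap is the missing effect measure.

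**The 30% is only a pooled planning figure.** Also true. A reader might infer that the median cannot be reached in either arm. The documents do not support that: more use is expected in placebo, the event also counts dose increases, and the early starts point above 30%.

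**Dropout as a competing event.** A reader might infer that Kaplan-Meier would overstate the cumulative start rate, or that the log-rank test conflicts with the primary model. Neither follows. The SAP plans no one-minus-Kaplan-Meier rate. Leaving the study ends observation but does not prevent a later start, so 31.8% lies within the possible 30% to 40%. A log-rank test with dropouts censored compares cause-specific hazards, the scale that the primary model's Cox parts also use. An Aalen-Johansen estimate would not correct informative dropout. What stands is that the handling of dropout is unstated here and differs between the other two analyses.

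**Conclusion.** The point holds for the effect measure. At the SAP's 30% starts and 10% loss, survival at week 36 is about 0.68. The median is not expected to be reached overall or on omega-3, and is uncertain on placebo (7% to 32% of simulated trials at 10% dropout under the two unequal splits). A comparison of medians is then unavailable, and the endpoint is left without an effect estimate or confidence interval for timing, contrary to the SAP's general rule.

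This rests on the 30% pooled figure, on roughly constant hazards and, for the arms, on assumed splits. The early-data extrapolation, at a higher rate, still places the pooled median after week 36. It is a moderate issue on one secondary endpoint and leaves the log-rank result and the primary analysis unchanged.

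**What to change.** In SAP section 7.2.1, for time to new or increased antidepressant use:

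1. Name an effect measure with 95% CI: a Cox cause-specific hazard ratio adjusted for the minimisation factors, or the difference in restricted mean time to week 36.
2. Add the week-36 cumulative probability of the event per arm and the difference between arms, with 95% CIs.
3. Report the median only where it is reached, and keep the log-rank test.
4. State that study dropouts are censored and that the analysis is therefore cause-specific.
5. Add a simple sensitivity analysis for informative dropout, such as bounds in which no dropouts, or all dropouts, start an antidepressant.

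The cost is a few lines of SAP text and a little more analysis. No new data are needed.
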